5.2 Analysis Sets

Three main analysis sets will be used: the Safety Analysis Set (SafAS), the Full Analysis Set (FAS), and the Per-Protocol Analysis Set (PPAS).

5.2.1 Safety Analysis Set

The SafAS is defined as those subjects who have received at least 1 dose of the study vaccine^b. Subjects will have their safety data analyzed after “any dose” according to the vaccine they actually received as the first dose. Safety analysis after each dose will be assessed in the subset of the SafAS having received that dose. Subjects will have their safety data analyzed after each vaccination according to the vaccine they actually received for that dose.

5.2.2 Full Analysis Set

The FAS is defined as the subset of subjects who received at least 1 dose of the study vaccine and have a valid post-vaccination blood sample result for at least 1 strain.

5.2.3 Per-Protocol Analysis Set

The PPAS is a subset of the FAS. The subjects presenting with at least 1 of the following relevant protocol deviations will be excluded from the PPAS:

- Subjects did not provide a post-dose serology sample

^a Post-final vaccination in each of the immunogenicity parameters is defined as 28 (window, 28–35) days post-final vaccination for subjects 6 months to < 9 years of age, and 21 (window, 21–28) days post-vaccination for subjects ≥ 18 years of age.

^b for which safety data are scheduled to be collected

- Subject did not meet all protocol-specified inclusion criteria or met at least 1 of the protocol-specified exclusion criteria
- Subject did not complete the vaccination schedule
- Subject received a vaccine or dose other than the one that he/she was assigned to receive
- Preparation and/or administration of vaccine was not done as per-protocol
- Subject did not receive vaccine in the proper time window
- Subject did not provide a post-dose serology sample in the proper time window
The proper time window for Group 1 and Group 2 is 28–35 days after final vaccination, and for Group 3, Group 4 and Group 5, the proper time window is 21–28 days post-vaccination.
- Subject received a protocol-prohibited therapy/medication/vaccine that might impact antibody response to the study vaccine
- Any other deviation identified during conduct of the study and judged by the clinical team during data review as having a potential impact on the assessment of immunogenicity

In addition to the reasons listed above, subjects will also be excluded from the PPAS if their post-vaccination serology sample did not produce a valid test result for any antigen.

5.2.4 Other Analysis Set

Enrolled subjects

Enrolled subjects are subjects for whom a CRF has been created.

5.2.5 Populations Used in Analyses

Baseline and demographic analyses will be performed on all enrolled subjects and/or the analysis sets described above, as appropriate.

The safety analyses will be performed on the Safety Analysis Set.

The immunogenicity analyses will be performed on both the FAS and PPAS.

5.3 Handling of Missing Data and Outliers

5.3.1 Safety

No imputation of missing data will be conducted. All subjects with safety data and all safety data recorded in the CRFs will be included in the safety analyses. No search for outliers will be performed. In all subject listings, partial and missing data will be clearly indicated as missing.

5.3.1.1 Immediate

For unsolicited non-serious systemic AEs, a missing response to the “Immediate” field is assumed to have occurred after the 20-minute surveillance period and will not be imputed.

For SAEs recorded within 24 hours, missing or partially missing elapsed time from last vaccination will remain missing and not be imputed. Such SAEs will not be considered as immediate.

5.3.1.2 Causality

Missing causality (relationship) for unsolicited non-serious AEs and SAEs will be considered at the time of analysis as related to vaccination.

5.3.1.3 Measurements

Partially missing temperatures will be handled as described in Section 4.4.1.1.1.

5.3.1.4 Intensity

For solicited reactions, missing intensities will be handled as described in Section 4.4.1.1.1. For unsolicited non-serious AEs, missing intensities will remain missing and will not be imputed.

5.3.1.5 Start Date and Stop Date

Missing or partially missing start dates for unsolicited AEs will remain missing and not be imputed. If either the start or stop date is missing or partially missing, the time of onset will be considered to be missing. Nevertheless, unsolicited AEs with missing time of onset will be included in analyses according to the visit at which the AEs were collected.

Missing or partially missing stop dates for AEs (solicited reactions and unsolicited AEs) will remain missing and not be imputed.

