9.3.1.2 Safety Endpoints

The observational endpoints for the evaluation of safety are:

- 1) Occurrence, nature (Medical Dictionary for Regulatory Activities [MedDRA] preferred term), duration, intensity, and relationship to vaccination of any unsolicited systemic AEs reported in the 20 minutes after vaccination.
- 2) Occurrence, time to onset, number of days of occurrence, intensity, action taken, and whether the reaction led to early termination from the study, of solicited injection site reactions (prelisted in the subject’s diary card and CRB) occurring from Day 0 through Day 7 after vaccination.
- 3) Occurrence, time to onset, number of days of occurrence, intensity, action taken, and whether the reaction led to early termination from the study, of solicited systemic reactions (prelisted in the subject’s diary card and CRB) occurring from Day 0 through Day 7 after vaccination.
- 4) Occurrence, nature (MedDRA preferred term), time to onset, duration, intensity, action taken, relationship to vaccination (for systemic AEs only), and whether the event led to early termination from the study, of unsolicited AEs from Visit 1 through Visit 2 for subjects receiving 1 dose or from Visit 1 through Visit 3 for subjects receiving 2 doses.
- 5) Occurrence, nature (MedDRA preferred term), time to onset, seriousness criteria, relationship to vaccination, outcome, and whether the SAE led to early termination from the study, of SAEs from Visit 1 through Visit 2 for subjects receiving 1 dose or from Visit 1 through Visit 3 for subjects receiving 2 doses.

Adverse events of special interest will be captured as SAEs. These include new onset of GBS, encephalitis/myelitis (including transverse myelitis), neuritis (including Bell’s palsy, optic neuritis, and brachial neuritis), thrombocytopenia, vasculitis, convulsions (including febrile convulsions [children only]), and anaphylaxis or other hypersensitivity/allergic reactions from Visit 1 through Visit 2 for subjects receiving 1 dose of vaccine, or from Visit 1 through Visit 3 for subjects receiving 2 doses of vaccine.

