9.3.1.3.3 Unsolicited Adverse Events

In addition to recording solicited reactions, subjects or subjects’ parents/guardians will be instructed to record any other medical events that may occur from Visit 1 through Visit 2 (Diary Card 1) for all subjects and from Visit 2 through Visit 3 (Diary Card 2) for subjects receiving 2 doses of study vaccine. Space will be provided in the diary card for this purpose.

Information on SAEs will be collected and assessed throughout the study, from Visit 1 through Visit 2 for subjects receiving 1 dose of study vaccine, and from Visit 1 through Visit 3 for subjects receiving 2 doses of study vaccine.

Any SAE occurring at any time during the study will be reported by the Investigator in the CRB according to the completion instructions provided by the Sponsor; this includes checking the “Serious” box on the AE CRF and completing the appropriate Death/Safety Complementary Information CRFs. All information concerning the SAE is to be reported either as part of the initial reporting or during follow-up reporting if relevant information became available later (e.g., outcome, medical history, results of investigations, copy of hospitalization reports). See [Section 10](#) for further details on SAE reporting.

For each unsolicited AE (whether serious or non-serious), the following information is to be recorded:

- Start and stop dates^a
- Intensity of the event:

For measurable unsolicited AEs that are part of the list of solicited reactions, the size of the AE as well as the temperature for fever will be collected and analyzed based on the corresponding scale used for solicited reactions (see [Table 9.1](#), [Table 9.2](#), [Table 9.3](#), [Table 9.4](#), and [Table 9.5](#)).

^a The stop date of all related AEs will be actively solicited. For other events, the Investigator will provide the stop date when it becomes available. AEs for which no stop date was obtained during the course of the study will be considered as ongoing at the end of the study.

All other unsolicited AEs will be classified according to the following intensity scale:

- Grade 1: A type of AE that is usually transient and may require only minimal treatment or therapeutic intervention. The event does not generally interfere with usual activities of daily living.

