4.4.1.2.4 Time of Onset

Time of onset is derived from the start date of the unsolicited non-serious AE provided in the clinical database and the date of last vaccination:

- start date of the unsolicited non-serious AE – date of previous vaccination

The time of onset should be considered as missing only if 1 or both of the dates are missing or partially missing.

An AE with missing time of onset will be considered to have occurred just after the vaccination indicated by the visit number and will be included in these tables. For subjects who received 2 doses, the worst-case scenario will be used for the post-any dose summary (i.e., the shorter time to onset period will be used if present for both doses or the available time to onset period will be used if present for either dose).

Note: Unsolicited non-serious AE that occurred before vaccination (negative time of onset) will not be included in analysis, but will be listed separately.

Time of onset will be displayed as follows:

- D0–D3
- D4–D7
- D8–D14
- \geq D15
- Missing

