4.4.1.2.5 Duration

Duration is derived from the start and stop dates of the unsolicited non-serious AE provided in the clinical database:

- stop date of unsolicited non-serious AE - start date of unsolicited non-serious AE + 1.

The duration should be considered as missing only if 1 or both of the start and stop dates of the unsolicited non-serious AE is missing or partially missing. For subjects who received 2 doses, the worst-case scenario will be used for the post-any dose summary (i.e., the longer duration will be used if present for both doses or the available duration will be used if present for either dose).

Duration will be displayed by period as following:

- 1–3 days
- 4–7 days
- 8–14 days
- \geq 15 days
- Missing

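### SAP 5.3.1.5 sets time of onset to missing when only the AE stop date is missing, contradicting the onset derivation in SAP 4.4.1.2.4

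*SAP*

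**What the plan says.** Two places in the SAP define when time of onset of an unsolicited AE is missing.

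- **SAP 4.4.1.2.4** names the source dates: "Time of onset is derived from the start date of the unsolicited non-serious AE provided in the clinical database and the date of last vaccination". The formula is the AE start date minus the date of the previous vaccination, and the rule that follows is "The time of onset should be considered as missing only if 1 or both of the dates are missing or partially missing". The dates in question are the AE start date and the vaccination date.
- **SAP 5.3.1.5** has a different rule: "If either the start or stop date is missing or partially missing, the time of onset will be considered to be missing". The vaccination date is not mentioned. The section also leaves missing stop dates unimputed and keeps AEs with missing onset in the analyses by visit.

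Three other places bear on this:

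- SAP 4.4.1.2.5 uses the start/stop pair for a different variable: "The duration should be considered as missing only if 1 or both of the start and stop dates" is incomplete.
- SAP 4.4.1.3.2 applies the onset method of 4.4.1.2.4 to SAEs.
- Protocol 9.3.1.3.3, footnote a, expects some stop dates to be absent when the study closes: "AEs for which no stop date was obtained during the course of the study will be considered as ongoing". For one class of events it tries to prevent this: "The stop date of all related AEs will be actively solicited".

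Time to onset is named in safety endpoints 4 (unsolicited AEs) and 5 (SAEs) of Protocol 9.3.1.2. SAP 4.4.1.2.4 gives it five display rows: D0–D3, D4–D7, D8–D14, D15 or later, and Missing.

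**The concern.** The stop date has no role in computing onset, so making onset depend on it discards a value that is available. The condition in 5.3.1.5 is the one that belongs to duration, which suggests it was carried over from there; that is an inference.

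Two programmers, each following one of the sections, would produce different onset tables from the same data. The loss under 5.3.1.5 would not be random. AEs that start late have less time to resolve before the last visit, so they are more likely to lack a stop date. The loss should also fall mainly on AEs judged unrelated, because stop dates of related AEs are pursued.

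There is one narrow effect on inclusion. SAP 4.4.1.2.4 removes pre-vaccination events through their negative onset: "Unsolicited non-serious AE that occurred before vaccination (negative time of onset) will not be included in analysis, but will be listed separately". An AE with a known pre-vaccination start and no stop date would have its onset set to missing under 5.3.1.5. The negative value that excludes it would be gone, and it would be counted by visit.

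**Working it through.** **Step 1: the two rules, by pattern of missing dates.**

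| AE start | AE stop | Vaccination date | SAP 4.4.1.2.4 | SAP 5.3.1.5 |
|---|---|---|---|---|
| known | known | known | onset computed | onset computed |
| missing | any | known | Missing | Missing |
| known | missing | known | onset computed | Missing |
| known | known | missing | Missing | not addressed |

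The third row is the contradiction. An AE that starts 5 days after vaccination and is still ongoing at study end has onset 5 days (row D4–D7) under 4.4.1.2.4 and is Missing under 5.3.1.5. The word *only* in 4.4.1.2.4 excludes a stop-date trigger, and neither section refers to the other or states precedence.

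**Step 2: how much could be lost.** The plan has no figure to reproduce, and the documents give no AE onset or duration data. What follows is an illustration on assumed inputs.

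- Last visit *V*: Day 21 for adults, Day 28 for children receiving one dose (the nominal visit days in the protocol).
- AE duration: exponential with mean *m* = 5, 7 or 14 days (assumed).
- Onset density: uniform on 0 to *V*, or early-weighted, proportional to exp(−t/7) (assumed).
- An AE ongoing at the last visit has no stop date (assumed).

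The probability that onset is lost, given onset at day *t*, is exp(−(V − t)/m). Averaged over a window [a, b] with uniform onset this is

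m/(b − a) × [exp(−(V − b)/m) − exp(−(V − a)/m)].

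For adults with *m* = 7 and uniform onset:

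- Days 15–21: 7/6 × (1 − exp(−6/7)) = 1.1667 × 0.5756 = 67%
- Days 0–3: 7/3 × (exp(−18/7) − exp(−3)) = 2.3333 × (0.0764 − 0.0498) = 6%
- All: 7/21 × (1 − exp(−3)) = 0.3333 × 0.9502 = 32%
- Share of lost AEs that started Day 15 or later: (6/21 × 0.672)/0.317 = 61%, against 6/21 = 29% of all AEs

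With early-weighted onset and *m* = 7, the product of density and loss probability is the constant exp(−3), so:

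- Days 15–21: 6 exp(−3) / [7 (exp(−15/7) − exp(−3))] = 0.2987/0.4727 = 63%
- Days 0–3: 3 exp(−3) / [7 (1 − exp(−3/7))] = 0.1494/2.4399 = 6%
- All: 21 exp(−3) / [7 (1 − exp(−3))] = 1.0455/6.6515 = 16%
- Share of lost AEs that started Day 15 or later: 6/21 = 29%, against (exp(−15/7) − exp(−3))/(1 − exp(−3)) = 7% of all AEs

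Adults, all cases:

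| Onset | Mean duration (days) | Lost, start Day 15 or later | Lost, start Days 0–3 | Lost, all AEs | Day 15 or later: share of lost / of all |
|---|---|---|---|---|---|
| Uniform | 5 | 58% | 2% | 23% | 71% / 29% |
| Uniform | 7 | 67% | 6% | 32% | 61% / 29% |
| Uniform | 14 | 81% | 25% | 52% | 45% / 29% |
| Early | 5 | 53.5% | 2% | 9% | 42% / 7% |
| Early | 7 | 63% | 6% | 16% | 29% / 7% |
| Early | 14 | 79% | 25% | 36% | 15% / 7% |

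Children, one dose, *m* = 7: with uniform onset, 45% for Day 15 or later, 2% for Days 0–3 and 25% of all AEs; with early-weighted onset, 34%, 2% and 7%.

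Late-starting AEs are over-represented among the lost in every adult case, but they are not always the majority.

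**The case against.** The contradiction itself is not in dispute. The case on the other side concerns its weight.

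- **Limited consequence.** The study is descriptive, with no primary or secondary objectives. Affected AEs stay in the analyses, and the loss shows in the Missing row. SAP 5.1.3.1 lists time to onset for solicited reactions, which are derived from daily intensities and so are untouched; for unsolicited AEs it lists only nature and relationship. This stands as a limit on importance. It does not remove the affected output, because the endpoints name onset and SAP 4.4.1.2.4 sets its display rows.
- **A sensible programmer would follow 4.4.1.2.4.** It has the formula, and SAP 5.3.1.3 and 5.3.1.4 refer back to Section 4.4 for other missing data. This is plausible but not decisive: 5.3.1.5 contains no such reference, and for causality SAP 4.4.1.4.5 defers in the opposite direction, to Section 5.3.
- **The percentages rest on assumptions and lean high.** The protocol footnote lets the investigator supply stop dates of unrelated events when they become available, and Protocol 5.1.4 requires follow-up of AEs that led to discontinuation. Some AEs ongoing at the last visit will therefore gain a stop date. This stands.
- **The pre-vaccination case is marginal.** Pre-existing conditions are not reported as AEs unless they worsen, and diary recording starts after vaccination. This also stands.

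**Conclusion.** The concern holds. The two sections give different results for every unsolicited AE, serious or not, that has known start and vaccination dates but no complete stop date, and nothing in the SAP says which prevails. That conclusion rests on the text alone.

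The size depends on data the documents do not give. In the adult illustration between 9% and 52% of onsets would be lost overall, with losses of 53.5% to 81% for AEs starting Day 15 or later against 2% to 25% for Days 0–3. These are nearer an upper bound for the chosen durations.

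The effect is confined to the onset distribution; incidence does not change except in the marginal pre-vaccination case. This is a consistency error that should be corrected, not a threat to the study's conclusions.

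**What to change.** Replace the sentence in SAP 5.3.1.5 with text such as:

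> Time of onset of an unsolicited AE, including an SAE, is set to missing only when the AE start date or the date of the preceding vaccination is absent or incomplete. An absent or incomplete stop date affects the duration alone, which is then missing (Section 4.4.1.2.5).

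Naming unsolicited AEs and SAEs keeps the sentence clear of the separate stop-date rule for solicited reactions in SAP 4.4.1.1.6. The rules that use the visit number to identify the last vaccination (SAP 4.4.1.2.3 and 4.4.1.3.1) stay as they are.

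The cost is one sentence. No new data are needed and no other derivation changes. The revised text agrees with SAP 4.4.1.2.4, 4.4.1.2.5 and 4.4.1.3.2.

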5.3.1.6 Action Taken

Missing actions taken will remain missing and not be imputed.

5.3.2 Immunogenicity

Missing data will not be imputed. No search for outliers will be performed.

In order to appropriately manage extreme values (undetectable responses $<$ LLOQ and \geq upper limit of quantitation [ULOQ]), the computational rule described in section 4.4.2.1 is applied.

The derived endpoint of fold-rise is computed as described in Section 4.4.2.3 for extreme values.

5.3.3 Efficacy

Not applicable

5.4 Interim/Preliminary Analysis

No planned interim /preliminary analyses are planned.

5.5 Determination of Sample Size and Power Calculation

The study will enroll approximately 240 subjects: approximately 30 subjects 6 to < 36 months of age will be administered Fluzone Quadrivalent vaccine (Group 1), approximately 30 subjects 3 to < 9 years of age will be administered Fluzone Quadrivalent vaccine (Group 2), approximately 60 subjects 18 to < 65 years of age will be administered Fluzone Quadrivalent vaccine (Group 3), approximately 60 subjects 18 to < 65 years of age will be administered Flublok Quadrivalent vaccine (Group 4), and approximately 60 subjects ≥ 65 years of age will be administered Fluzone High-Dose vaccine (Group 5).

No sample size calculations were performed. Only descriptive statistical analyses will be conducted in this study.

5.6 Data Review for Statistical Purposes

A review of the data is anticipated through the data review process led by Clinical Data Management before database lock. This review of the data includes a statistical review.

